4. A clinically unstable medical condition in the previous 2 months as defined by a new medical diagnosis (e.g., pneumonia, cardiac disease, thyroid disease, depression or psychosis, cirrhosis, cancer, etc.)
5. Individuals who regularly experience jet lag or irregular work schedules over the previous 3 months
6. Women who are pregnant or women who are sexually active and of child-bearing age who are not using some form of contraceptive
7. *Unable to perform tests due to visual (inability to read the consent form) or hearing (unable to have a phone conversation) impairment, or unable to perform activities of daily living*

Participants will complete the following baseline questionnaires on the website: FOSQ-10, EES, SF-12, CES-D, EQ-5D (including the EuroQol feeling thermometer), and medical service use not captured by their electronic medical record (Table 2 and Appendix 3). The Charlson comorbidity index will be used to determine if health status predicts which patients are good candidates for REVAMP management.

To monitor for possible selection bias, all potential participants will be tracked to determine the number who agree to be contacted, the number who provide informed consent, the criteria that excluded an individual's participation, and the reasons why participants were unable to complete the protocol. Post-hoc analysis will compare patient characteristics at baseline to assess for any differences across groups and sites. Following completion of the baseline questionnaires, the CES-D score will be reviewed by a member of the research team who is not involved with delivery of care. The participant's primary care provider will be notified if the CES-D score is greater than 24, indicating the presence of severe depression. These participants will be allowed to continue in the study since all participants with OSA will receive APAP treatment and this intervention has been shown to improve depression. To assess for any medication changes that might affect functional outcomes, a list of the participant's medications, with their dosage and frequency, will be obtained from the patient and the patient's medical record during the first 3 months of PAP treatment.

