All participants will complete the website questionnaires in order to standardize collection of our functional outcomes. Practitioners in both arms will not have access to the responses to the patient satisfaction questionnaires (WAI-SR and CSQ-8). The other questionnaire responses of the participants randomized to REVAMP management will be available to the practitioners performing the phone clinic evaluations. Enrolled subjects assigned to the in-person arm will only have access to the website's questionnaires but none of its other features. They will be informed that a research staff member will contact them to schedule their first clinic appointment. None of the questionnaires they complete on the website will be shared with their practitioners. At the time of their in-person clinic visits, these participants will complete the questionnaires that are routinely used as a part of the clinical site's usual care. That information will not be collected for analysis.

**Table 2.** Data collection and action schedule for all participants

Measures & Procedures	Baseline assessment	Initial clinical assessment	AutoCPAP set-up	1-week phone FU	1-month FU assessment	3-month FU assessment
	Week 0	Week 2-4	Week 8	Week 9-12	Week 12	Week 20
Eligibility criteria	In-person					
Informed consent	In-person					
Patient characteristic questionnaire	website					
Functional & QOL questionnaires†	website				website	Website Δ
Therapy process indicators‡		website		website	website	Website Δ
Clinical assessment*		In-person vs phone		Phone	In-person vs phone	In-person vs phone
APAP set-up			DME			
APAP adherence*				Wireless	Wireless	Wireless

DME = home health care company; FU=follow-up; QO =quality of life; Δ=performed every 3 months thereafter to the end of data collection

\* Subjects randomized to in-person management will have in-person clinic evaluations in the sleep center and subjects randomized to REVAMP management will have phone clinic sessions. APAP adherence in both groups will be obtained by wireless modem.

[figure not shown]
† Functional & QOL questionnaires: FOSQ-10, ESS, SF-12, CES-D, and EQ-5D; ‡ Therapy process indicators: WAI, CSQ-8 (performed within 1-week following each encounter)

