**Participant randomization.** Upon completing baseline questionnaires, a computer-generated, blocked randomization scheme in the REVAMP program will automatically allocate eligible participants into one of two groups: *REVAMP management versus in-person management*. Randomization at each site will be programmed by SAS module Proc Plan. Block size at each site will be six subjects so that among each block of six randomized individuals, exactly three will be assigned to each group in a random order. Investigation and management of the two arms of care will be conducted over equal time periods.

**REVAMP pathway.** Following completion of the website questionnaires and the HST, REVAMP participants will be scheduled for an initial phone interview with the *sleep specialist (MD or NP)* (Fig 4). The practitioner will review the results with the subject. *Using the criteria required by the Center of Medicare and Medicaid Services, participants with AHI  $\geq 15$  events/hr and subjects with  $5 \leq AHI < 15$  who have OSA-related symptoms will be diagnosed with OSA.* Those interested in PAP treatment will be prescribed an APAP unit with wireless modem. Subjects with OSA who are found on follow-up to require bilevel PAP and/or supplemental oxygen will continue to participate in Aim 1. Participants testing negative for OSA will be offered usual clinical care to further evaluate their sleep-related symptoms. Participants with a diagnosis of central sleep apnea/Cheyne-Stokes respiration

(CSA/CSR) will be referred to a sleep physician and PSG testing. *Participants without OSA on HST and participants with CSA/ CSR will not be included in the Aim 1 modified intent to treat analysis set but will be included in the primary analysis set of Aim 2 and Aim 3.*

The wireless modem on the home PAP unit sends PAP data daily to the manufacturer's server which in turn exports the data daily to the REVAMP website. The website displays the following information in an easily understandable format: hours of use, amount of air leak, and AHI (Fig. 2). Participants and practitioners can view the data on the REVAMP website. Participants will be instructed to review their results on the website daily. The number of times a subject logs into the website will be tracked.

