Following the first week of PAP treatment, a therapist with at least one year of experience managing patients with OSA will phone the participant. Using a standardized protocol, the therapist will evaluate the participant's response to treatment, inquire if any barriers are limiting PAP use, and provide advice on how to overcome those problems (see *Appendix 4*). The therapist will encourage the participant to review his/her PAP data on the website. The participant will be scheduled for 1- and 3-month follow-up phone calls with the therapist. Additional phone calls are allowed as clinically indicated and will be tracked. The therapist will have the option of consulting with the sleep specialist (MD or NP). Upon consultation, if it is felt that the problem cannot be addressed by phone, the participant will be scheduled for an in-person clinic appointment with the physician. The type, number

and duration of all encounters will be recorded in case report forms. All phone clinic sessions and other patient encounters will be documented in the participant's electronic medical record.

REVAMP has a secure message system that sends e-mail and text messages to the participant alerting him/her to login to the website to view a message. The REVAMP website will use this feature to remind the participant to complete questionnaires, view their PAP data, and keep scheduled phone clinic appointments.

*In-person management.* Participants in the in-person arm will be scheduled to meet with the sleep therapist for in-person set-up instructions for HST. Following HST, a sleep specialist (MD or NP) will conduct the initial in-person clinic evaluation. Participants diagnosed with OSA (using the same criteria detailed above for the REVAMP pathway) who are willing to start PAP treatment will be prescribed APAP. Sleep therapists with at least one year of experience managing patients with OSA will perform the follow-up clinic evaluations. Participants will receive a 1-week phone call and be scheduled for 1- and 3-month in-person follow-up clinic visits. Additional phone calls and clinic visits will be allowed as clinically indicated. The type, number and duration of all encounters will be monitored and documented in the participant's electronic medical record.

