The clinical sites will use a type 3 portable monitor that records nasal pressure, rib cage and abdominal movement, pulse oximetry, and body position. Two of the sites use the T3 monitor (Nox Medical) and the third site uses Nomad, Nihon Kohden. We will control for diagnostic bias by ensuring that the sites record identical channels, at an identical sampling frequency. The monitor will be distributed to participants in the REVAMP arm without in-person set-up instructions, and they will be directed to the REVAMP website to review a video on OSA and PAP treatment developed by the American Sleep Apnea Association and a step-by-step instructional video and brochure explaining HST set-up (Appendix 2). Postal materials will be provided to mail the monitor back to the sleep center using a carrier that allows tracking of the package. Participants randomized to in-person management will be scheduled to meet with a technologist at the sleep center to receive in-person instructions on how to perform the test. During the visit, the subject will be shown the videos and provided with the set-up brochure (Appendix 2). The therapist will explain how to operate the monitor, demonstrate placement of the sensors, and answer the participant's questions. The patient will be given the option of returning the monitor by mail or in-person. Participants in both arms will be provided a 24/7 phone number to contact an on-call PSG technologist at the site's sleep center with any questions about the set-up.

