**Statistical methods for Aim 3, Quantitative component.** Aim 3 will compare patient-centered treatment acceptability and process measures of the two management approaches. We will evaluate patient acceptance of telemedicine-based care by comparing the between-group differences in attrition, therapeutic alliance, and satisfaction with care. The primary quantitative objective outcome measure in Aim 3 will be percent of patients who drop out of each treatment. The primary subjective outcome measures will be change in the WAI-SR and CSQ-8 scores. For this exploratory aim we will estimate mean values and confidence intervals. Mixed effects models will be used to estimate the between-groups difference in means and confidence intervals, for each of

the outcome measures. Results will be ascertained via ITT and per-protocol procedures as previously discussed. A series of mixed models is proposed for each outcome identified in Aim 3 (WAI-SR, CSQ-8).

Qualitative data analysis. Interviews will be digitally recorded with the participant's permission, transcribed by a professional transcriptionist, and prepared as primary documents to be loaded into Atlas.ti software for data management and analysis. Atlas.ti is a software program designed to assist in the management and analysis of qualitative data, including primary documents (e.g., transcripts), secondary notes (e.g., memos written by the investigators concerning methodological issues), and analytical notes (e.g., emerging theories to be tested through further data collection and analysis). Atlas is particularly suited to the constant comparative method most closely associated with grounded theory, adapted for use in healthcare and health services research. Analysis of patient interviews will be guided by Aim 3: to identify patient perspectives, attitudes, and preferences regarding REVAMP versus in-person management of patients with OSA, as well as barriers and facilitators to participation in either clinical pathway. *Similarly, analysis of provider interviews will focus on identifying providers' attitudes and perspectives on acceptability of delivering care via REVAMP vs. in-person, and perceived barriers and facilitators to implementation, spread, and maintenance of REVAMP as a means to deliver treatment for patients with OSA.*

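### Aim 3 analyses change in WAI-SR and CSQ-8, but every score is taken after randomization and after an arm-specific encounter, so change removes any arm difference already present at the first score.

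*Combined protocol and SAP*

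**What the plan says.** **Outcome.** In STATISTICAL ANALYSIS, the quantitative component of Aim 3 states: "The primary subjective outcome measures will be change in the WAI-SR and CSQ-8 scores". No reference visit for the change is named. The same paragraph gives the goal as comparing attrition, alliance and satisfaction between groups. It calls the aim exploratory and plans mixed models for between-group differences in means.

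**Timing of the two scales.** The Table 2 footnote reads: "Therapy process indicators: WAI, CSQ-8 (performed within 1-week following each encounter". Their Week 0 cell is empty, and the first entry falls under the initial clinical assessment at Week 2-4. The list in the eligibility and enrollment text that opens "Participants will complete the following baseline questionnaires on the website: FOSQ-10" goes on to the Epworth scale, SF-12, CES-D, EQ-5D and medical service use. It contains neither WAI-SR nor CSQ-8.

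**Randomization.** Under Participant randomization: "Upon completing baseline questionnaires, a computer-generated, blocked randomization scheme in the REVAMP program will automatically allocate eligible participants into one of two groups".

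**First encounter.** Under REVAMP pathway, "REVAMP participants will be scheduled for an initial phone interview with the" sleep specialist. Under In-person management, "a sleep specialist (MD or NP) will conduct the initial in-person clinic evaluation". The Table 2 footnote describes clinical assessments generally in the same way: "Subjects randomized to in-person management will have in-person clinic evaluations in the sleep center and subjects randomized to REVAMP management will have phone clinic sessions". Home sleep test set-up comes earlier and also differs: "The monitor will be distributed to participants in the REVAMP arm without in-person set-up instructions", while the comparator arm attends the sleep center for instruction.

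**The concern.** A change score is a sound randomized comparison when the starting value is measured before the arms diverge, because the expected arm difference at the start is then zero. Here the earliest available score is itself an outcome of the assigned mode of care. Subtracting it removes whatever the mode of care has already done to alliance or satisfaction.

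The first contact is a plausible place for a phone-versus-in-person difference to appear. If it appears there and persists, both arms show the same change and the named primary subjective outcomes show nothing. Aim 3 would then report an estimate and interval for a quantity other than the one it set out to measure. A larger sample would not help, because the problem lies in what is estimated and not in its precision.

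**Working it through.** **1. Order of events.** Taken from the sections cited above:

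| Step | REVAMP | In-person | WAI-SR / CSQ-8? |
|---|---|---|---|
| Baseline questionnaires, Week 0 | website | website | No |
| Randomization | on completing them | on completing them | No |
| Home sleep test set-up | no in-person instruction | visit to the center | No |
| Initial clinical assessment, Week 2-4 | phone | in person | **First score** |
| 1-week follow-up | phone | phone | Yes |
| 1- and 3-month follow-up | phone | in person | Yes |

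The baseline list, the Table 2 row and its footnote agree, so the reading does not depend on how one table cell was extracted. Every scheduled score follows randomization, so whichever visit is chosen as the reference, the same difficulty arises.

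**2. What change estimates.** Let d1 be the arm difference in mean score after the initial assessment and d3 the difference at month 3. Then:

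- level at month 3 estimates d3;
- change from the first score estimates d3 − d1;
- month 3 adjusted for the first score as a covariate estimates d3 − ρ·d1, where ρ is the within-arm correlation of the two scores (equal SDs).

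Only the first is the between-group difference in alliance or satisfaction at that visit.

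**3. Size.** The documents give no SD, effect size or power for either scale, so there is no figure of the plan's to reproduce. Assume SD = 1 and let f be the share of d3 already present at the first score (d1 = f·d3). The change contrast is d3·(1 − f):

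| Assumed d3 | f = 0% | f = 50% | f = 100% |
|---|---|---|---|
| 0.3 SD | 0.30 | 0.15 | 0 |
| 0.4 SD | 0.40 | 0.20 | 0 |
| 0.5 SD | 0.50 | 0.25 | 0 |

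These contrasts do not depend on ρ.

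Covariate adjustment does not avoid the problem. With d3 = 0.4, d1 = 0.2 and ρ = 0.5 it gives 0.4 − 0.5 × 0.2 = 0.30, not 0.40. For ρ from 0.3 to 0.7 it gives 0.34 to 0.26.

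**4. Against the likely precision.** 356 randomized is 178 per arm. Applying the plan's own 20% without OSA and 20% drop-out gives 178 × 0.8 × 0.8 ≈ 114 per arm at month 3. The standard error of a level difference is √(2/114) = 0.132 SD, and the 95% half-width is 1.96 × 0.132 ≈ 0.26 SD. The change-score SD is √(2(1 − ρ)), which equals 1 at ρ = 0.5, so the half-width is the same there.

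With d3 = 0.4, the expected interval for level is 0.14 to 0.66. For change it is −0.06 to 0.46 at f = 50% and −0.26 to 0.26 at f = 100%.

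**The case against.** **The surrounding text points to levels.** The Aim 3 analysis paragraph speaks of mean values and of between-group differences in means. Nothing says that the first score will be subtracted or used as a covariate. This is fair, and it means subtraction from the first score is the natural reading of the word change rather than a stated computation. It does not remove the defect. The outcome named is change, and no scheduled score could serve as a pre-intervention reference. If levels are intended, the sentence needs correcting all the same.

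**The effect need not be constant.** The first encounter is with a sleep specialist, whereas follow-up is by a therapist, and the 1-week call is by phone in both arms. The provider being rated and the contrast in mode both vary over visits. This stands: a reader might infer that change removes the whole effect, but that is true only if the difference is fully present at the first score and persists unchanged.

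**Consequences are limited.** A reader might infer that the acceptability conclusion would be reversed. The algebra allows d3 − d1 to take the opposite sign to d3 if an early gap narrows, but nothing in the documents indicates that pattern. Aim 3 is exploratory, has no margin or decision rule, and also draws on attrition and on patient and practitioner interviews. Reversal is not supported.

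**Add a baseline instead.** A score before any care would mean little. WAI-SR rates a working relationship and CSQ-8 rates services received, and neither exists at Week 0.

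**Conclusion.** The point holds as a wrong outcome definition. The timing is clear from several places in the document. Followed as written, with the first available score as reference, the primary subjective Aim 3 outcomes estimate d3 − d1 and not the between-group difference the aim asks about.

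The loss equals the part of the difference present at the first score: from none to all of it, or 0 to 0.4 SD under an assumed month-3 difference of 0.4 SD. That effect size, the unit SD and the shares tried are illustrations and do not come from the documents.

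The effect is confined to the two subjective outcomes of an exploratory aim. Attrition, the interviews, and Aims 1 and 2 are untouched. It should be corrected because these are the named primary subjective outcomes and the correction is simple.

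**What to change.** In the quantitative component of Aim 3, replace the change wording with the WAI-SR and CSQ-8 score levels. Analyse each scale with a mixed model of all post-encounter scores, with terms for treatment, visit, treatment-by-visit and site. Do not subtract the first score or adjust for it.

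Report the arm difference in means with a confidence interval at each visit, including:

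- **After the initial assessment.** The REVAMP pathway section keeps participants without OSA, or with central sleep apnea/Cheyne-Stokes respiration, in the Aim 3 primary analysis set. Those who never start APAP may have no later encounter to rate, so this visit covers them.
- **At month 3, among participants who had that encounter.** Label it as such, since the follow-up visits in Table 2 come after APAP set-up.

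Change from the first encounter may be kept as a secondary description, labelled as change between two post-randomization scores.

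The cost is a wording edit to the analysis section. The questionnaires and their schedule stay as they are, and no new data are needed.
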